## 5.4 Dosage and Adherence Samples

The dosage exploratory analysis will include everyone with a 3-month outcome for the SA, EA, and UMC groups. We will use the number of acupuncture treatments received regardless of which group a person was randomized to as their dose. For adherence analyses we will include 1) participants in the acupuncture groups who, in the 3 months of standard acupuncture, received at least 8 treatments and the last visit indicated that they had completed treatment or received at least 12 treatments and 2) amongst those with last visit indicated that they had completed treatment (see Protocol section 5.4. for our proposed operationalization criteria for "completed treatment").

## 6. Definition of Treatment Adherence

Treatment adherence in SA group is defined as (1) receiving a minimum of 8 acupuncture treatment in the 3-month of standard acupuncture period with the last clinical visit indicating a completion of treatment or (2) receiving at least 12 acupuncture treatments in the standard acupuncture period. For EA group, treatment

adherence is defined as, in addition to the adherence defined in SA group, (1) receiving at least 4 maintenance acupuncture or (2) a note of completion remarked by acupuncturists. Participants who are randomized to the EA group will be asked to attend the maintenance visits.

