5. STUDY INTERVENTIONS

5.1 Interventions, Administration, and Duration

Acupuncture will be individually administered to patients by a licensed acupuncture practitioner in outpatient HCSs clinics or community acupuncturists' offices.

5.1.1. Standard acupuncture (SA):

Our SA intervention is based on classical Chinese acupuncture therapy and was developed with a team of experts using a modified Delphi process. It involves up to 15 acupuncture treatments over 3 months with the total number being determined by the patient and acupuncturist together. (Fifteen treatments is consistent with the greatest number of allowed treatments in some of the largest acupuncture trials to date.²⁸⁻³⁰) We encourage, however, a minimum of 6-8 treatments in the first 8 weeks,^{23,42} with at least 1-2 treatments in the last 4 weeks.^{24,25} The Acupuncture Advisory Panel recommended that we consider 8 treatments as the minimum for determining if the patient is not a responder to acupuncture. Treatment visits will typically last 45-60 minutes. All treatments will include only acupuncture needling, even though other adjunctive modalities (e.g., moxibustion or other forms of heat, cupping, gua sha, tui na) are typically part of practice.⁴³ Treatments will be provided at medical facilities or in private acupuncturists' offices.

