Acupuncturists will have at least five years of experience working at least 50% of the time in patient care. There may be exceptions for 3 years' experience per individual applicant, for example with other health care licensure. They will need to be state licensed, malpractice insured (with no current or historic malpractice claims) and experienced in treating patients with chronic low back pain and who have multi-morbidities. They will also need to be experienced working with older adults. In addition to the above, they will be vetted by the health plans and/or lead acupuncturist (for example, at KPWA, we will recruit from our network of providers and at IFH, we will recruit from prior trials). They will all be trained in the protection of Human Subjects for research, as well as the study protocol, special safety issues for our study, and the logistics of delivering and recording study treatments. They will be certified for participation in the study.

Capturing acupuncture treatment visit information:

As a pragmatic trial, patients are not required to complete all acupuncture visits to stay in the study. An intent-to-treat approach to analysis will be used. Data for each visit at KPNC, KPWA and SH will be collected from the treating acupuncturist in a secure, SQL server HIPAA-compliant online database, which in turn will trigger a payment to the acupuncturist for the acupuncture session. Acupuncturists working at IFH clinics will chart in the EHR using a specially designed EPIC template. Data will be securely submitted following each session with the following information: date, visit number, visit length, visit disposition (e.g., completed, cancelled, no show), elements of the visit (e.g., asking interview, palpation of acupoints), selected needling details (e.g., number of needles, retention time, acupoints needled, whether this was this the last recommended treatment), and patient reported adverse events. Based on

ours and others previous studies^{25,32,34}, we expect that patient reported AEs are most likely to involve minor pain, dizziness, itching or bruising after needling, transitory exacerbation of pain, or fatigue.

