We will assess adherence by several means: attendance at acupuncture visits and the content of those visits. Because different participants might require different numbers of visits, we will ask the acupuncturists at each visit to let us know whether the patient is continuing treatment, has completed treatment or is unlikely to improve (including before and after at least 8 treatments as recommended by the Acupuncture Advisory Panel). This will allow us to determine whether a patient stops treatment prematurely. Even patients who stop the treatment prematurely in the standard treatment period but are randomized to receive maintenance acupuncture will be encouraged to make acupuncture visits in the maintenance period. We will assess acupuncturists' fidelity to the treatment protocol by reviewing completed treatment forms at the end of each treatment session, which will include key details of their study visit, the structure of the visit, needling details and acupuncture points used, visit duration, and self-care recommendations (Appendix 2 has a copy of the form). We will also ask patients about their use of non-study acupuncture treatments to characterize any acupuncture received by participants outside study provided services.

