We will conduct a set of prespecified moderator analyses using a similar analysis as Aim 1 except include interactions with the moderator and treatment groups. Moderators of interest include age (65-74; 75-84; 85+), patient expectations and gender. However, we do not anticipate being powered to detect a difference in treatment effects between men and women. According to results from the Acupuncture Trialists Collaboration, gender has not been consistently found to be related to benefits from acupuncture.¹⁰⁵ We will look at race and ethnicity as well, but we will not be powered to detect a difference between groups. We have identified potentially important clinical conditions that may well diminish treatment effect (i.e., cognitive impairment, frail elderly, co-morbid pain conditions, co-morbid depression). If these are sufficiently common in our study participants, we will perform pre-specified moderator analyses.

We will also conduct exploratory per protocol analyses assessing dose response to see if the effect changes dependent upon number of acupuncture treatments received and include UMC as having 0 treatments in the analyses. We will flexibly model the trajectory of the primary outcome at 3 months by number of treatments to see if there is a threshold effect of treatment dose. Further we will run adherence analyses comparing amongst those who adhered in the 3-months of standard acupuncture (at least 8 treatments and last visit indicated by acupuncturist that they completed treatment or at least 12 treatments) compared to UMC and amongst those adhered to those who did not adhere within the acupuncture groups. We will do a second set of adherence analyses but define adhered as only those that the acupuncturist indicated as completing treatment. Since these analyses are not intent-to-treat we will include further potential confounders that are associated with being non-adherent or receiving differential number of treatments.

Aim 2: We will perform economic evaluations from both the payer (Medicare) and health care sector perspectives alongside the randomized pragmatic trial comparing usual medical care (UMC) to the addition of 3-months of acupuncture (SA) and 3-months of acupuncture and 3-

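### The adherence contrasts select patients on a post-randomisation code that can track response; label them descriptive and add a supportive complier-average estimate against usual care.

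*SAP*

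**What the plan says.** For the standard period, SAP 6 gives two routes to adherence: "receiving a minimum of 8 acupuncture treatment in the 3-month of standard acupuncture period with the last clinical visit indicating a completion of treatment", or at least 12 sessions whatever the code. SAP 15.2 compares adherers with UMC and with non-adherers. It then repeats the work counting as adherent only those whom the acupuncturist recorded as completing treatment.

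For the meaning of completed treatment, SAP 5.4 says "see Protocol section 5.4. for our proposed operationalization criteria for" that term. Protocol 5.4 has the treating acupuncturist declare completion and report at each visit "whether the patient is continuing treatment, has completed treatment or is unlikely to improve". Protocol 5.1, listing the data captured per visit, instead mentions "whether this was this the last recommended treatment". It also lists "visit disposition (e.g., completed, cancelled, no show", which concerns attendance.

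Session number is flexible, "with the total number being determined by the patient and acupuncturist together" (Protocol 5.1.1). For the dose analysis, SAP 5.4 takes the "number of acupuncture treatments received regardless of which group a person was randomized to as their dose", whereas Protocol 9.6 will "include UMC as having 0 treatments in the analyses". SAP 17 also assigns UMC zero in its dose-response analyses of secondary outcomes.

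Protocol 9.3 and 9.6 call the per-protocol work exploratory. SAP 15.2 says the analyses are not intent-to-treat and adds confounders. It does not call the adherence contrasts exploratory, although SAP 15.1 does so for the moderators.

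**The concern.** The code that defines adherence is assigned after randomisation by someone watching the patient's progress. Three places in the protocol make a link with response plausible. Protocol 5.4 sets completion apart from being unlikely to improve. Protocol 5.1.1 reports 8 sessions as the advisory panel's minimum for judging non-response. Protocol 10.3.1 trains acupuncturists on when to stop for failure to respond. If patients who are doing well tend to be coded completed, adherers look better than UMC and than non-adherers even if acupuncture does nothing. If patients who do well stop early, the reverse can happen.

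Adjustment for predictors of non-adherence removes only the selection those predictors explain. It does not remove selection on response during treatment. The dose model avoids the code, but session number is also settled after randomisation. So no planned adherence or dose analysis keeps the randomised comparison, and neither document contains a complier-average or instrumental-variable estimate.

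At stake is how a secondary finding is read: a reader could take a selection artefact for the effect of a full course.

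**Working it through.** **The plan's own figure.** The adherence sections state no number. SAP 4 gives a 95% CI half-width of 1.15 for two groups of 210 at SD 6: 1.96 × 6 × √(2/210) = 1.15. It reproduces.

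**Inputs from the documents.** SD of RMDQ change 5.11 (SAP 4, 6-month change in one earlier trial, applied here at 3 months); 210 per arm with data, so 420 in SA and EA pooled.

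**Assumptions.** No true effect. J is a standard normal measure of perceived response, correlated rho = 0.5 with RMDQ improvement. 50% reach 12 or more sessions, 40% end at 8 to 11 and 10% below 8, all independent of outcome. Covariate adjustment and clustering are not modelled. SAP 15.2 names 3 months for the dose model only. A plus sign favours acupuncture. One unit of J is worth 0.5 × 5.11 = 2.555 points.

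**Main definition, coding strictly by response (completed if J > 0).**
- Mean J in completers is 0.798. Adherers are 50% + 20% = 70%, with mean J = 0.2 × 0.798 / 0.7 = 0.228. Against UMC: 0.228 × 2.555 = **+0.58**.
- Non-adherers are 30%, with mean J = -0.2 × 0.798 / 0.3 = -0.532. Against non-adherers: (0.228 + 0.532) × 2.555 = **+1.94**.

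**Other codings.** Noisy coding (completed if J + N(0,1) > 0) has mean J 0.798/√2 = 0.564 in completers. The false-benefit rate is 1 − Φ(1.96 − bias/SE), using subgroup variances; its nominal value is 2.5%.

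| Main definition | vs UMC | vs non-adherent | false benefit |
|---|---|---|---|
| Strict | +0.58 | +1.94 | 24% / 96% |
| Noisy | +0.41 | +1.37 | 14% / 73% |
| Noisy, half of the 8–11 group still continuing | +0.24 | +0.60 | 7% / 22% |
| Everyone at 8–11 counted as completed | 0 | 0 | 2.5% / 2.5% |

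The last row is what the last-recommended-treatment item would give if it were marked whatever the reason for stopping. Over rho 0.3 to 0.7, three splits (50/40, 30/55 and 60/25% at 12+ / 8–11) and the first three codings, the range is +0.08 to +1.4 against UMC and about +0.25 to +3.2 against non-adherers.

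**Completed-only set** (same central case, code applied to everyone with 8 or more sessions).
- Strict, against UMC: 0.798 × 2.555 = **+2.04**.
- Non-completers are 55%, with mean J = -0.45 × 0.798 / 0.55 = -0.653. Against them: (0.798 + 0.653) × 2.555 = **+3.71**.
- Noisy: 0.564 × 2.555 = +1.44, and (0.564 + 0.45 × 0.564 / 0.55) × 2.555 = +2.62.

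**Patterns that reduce or reverse the main-definition bias.**
- Slower responders go on to 12 or more sessions (session rank correlated -0.4 with J, noisy coding; 4,000,000 simulated patients): -0.03 / -0.13 if early stopping follows the same ranking, +0.15 / +0.58 if it is random.
- The best 10% finish before session 8, the worst 5% are stopped at 8 to 11 and 10% lapse at random: -0.2 / -0.9.

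**Complier-average estimate.** It equals the intent-to-treat difference divided by (π − q), where π and q are the shares receiving acupuncture in the acupuncture arms and in UMC. With no effect the numerator has expectation zero, so no stopping pattern biases it. SE = 5.11 × √(1/420 + 1/210) / (π − q) = 0.432 / (π − q).

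| π | q | SE |
|---|---|---|
| intent-to-treat | – | 0.43 |
| 0.95 | 0 | 0.45 |
| 0.85 | 0 | 0.51 |
| 0.95 | 0.05 | 0.48 |
| 0.85 | 0.10 | 0.58 |

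- If UMC crossover is missed, a true 2-point effect reads as 2(π − q)/π. At π = 0.90 that is 1.9 for q = 0.05 and 1.8 for q = 0.10.
- With an 8-session cut as exposure, a 2-point effect is overstated by (1 − π)/π × k, where k is the effect of 1 to 7 sessions. For π of 0.90 to 0.70 this is 0.11–0.43 at k = 1 and 0.22–0.86 at k = 2.

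**The case against.** The strongest reply has four parts.

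1. The source of the code is identified. A reader might infer that the plan never says where completion comes from. It does: SAP 5.4 refers to Protocol 5.4, which names the acupuncturist and a three-way status. The visit form (Appendix 2) is not in the text supplied, so its absence proves nothing. What remains is to reconcile the two descriptions in Protocol 5.1 and 5.4.
2. The exploratory status is mostly in place. A reader might infer that these contrasts are offered as confirmatory. The protocol says otherwise, and no conclusion rule uses them. The gap is the missing label in SAP 15.2.
3. The sizes are assumed. This stands. Only the SD and group sizes come from the documents. A reader might infer that the contrasts will overstate benefit, or quote the 96% as a forecast. The documents give no stopping pattern, and plausible ones give zero or negative bias under the main definition. The completed-only set is less reassuring: in both slower-responder cases it stays above +1 against UMC, because it selects on the code directly.
4. An any-acupuncture complier estimate rescales intent-to-treat and says nothing about an adequate course. This also stands, so it should be supportive and should not replace the adherence comparison. It still gives an effect in those treated without selecting on response.

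**Conclusion.** The concern holds as a cheap improvement. The adherence contrasts, above all the completed-only set, select on a post-randomisation code that can track response, and baseline adjustment does not cure that. With no true effect they can show a benefit, a harm or nothing. In the central case the main definition gives 0 to +0.6 points against UMC and 0 to +1.9 against non-adherers, and one other stopping pattern gives -0.2 / -0.9. Strict coding in the completed-only set gives about +2.0 / +3.7, around or above the plan's 2-point MCID. These are illustrations at SD 5.11 with assumed visit splits, coding and rho.

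A reader might infer that the trial's main conclusion is at risk. It is not: the primary analysis is by intent-to-treat at 6 months and does not use the code.

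The difference over UMC exposure between SAP 5.4 on one side and Protocol 9.6 and SAP 17 on the other needs no assumptions, and should be settled before unblinding.

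**What to change.** All changes concern analysis only; the planned adherence definition stays.

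1. **SAP 15.2, label.** Call the adherence contrasts, including the completed-only set, exploratory and descriptive.
2. **SAP 15.2, addition.** Add a supportive complier-average estimate against UMC at 3 months, SA and EA pooled, with randomisation as the instrument and the covariates and missing-data handling of SAP 9 and 13. Exposure: any acupuncture received, study or non-study, in both arms. Alternative: number of visits as a continuous exposure, assuming linearity. Do not use the completion code. Use the 8-visit cut as a sensitivity analysis only, since it assumes no effect of 1 to 7 visits.
3. **State the limits.** Assignment must act only through treatment received, which is open to question because participants are unmasked. The estimate is the effect in those treated. It is neither the effect of an adequate course nor a new test.
4. **Reconcile UMC exposure** across SAP 5.4, SAP 17 and Protocol 9.6. The named acupuncture-use item is asked at 12 months only (Protocol 6.2.2), so check the other recorded utilisation items. Show the estimate with and without UMC crossover counted as before 3 months.
5. **Minor clarifications.** State which item and value mean completed, reconciling Protocol 5.1 with 5.4. Align the non-adherer comparison, which SAP 15.2 confines to the SA groups and Protocol 9.6 applies to the acupuncture groups.

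The cost is SAP wording and one extra estimate from planned data, with no change to sample size or alpha. The downside is the modestly larger standard error shown above.

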### **Blinding**

This is an unmasked trial for participants, although the participants assigned to SA and EA will only know they are randomized to acupuncture groups at the time of randomization. Participants assigned to EA group will not be informed about additional maintenance treatment sessions until close to the end of the first 3 months of treatment (approximately 10 weeks into the study) so that their treatment is unlikely to be altered by the knowledge of additional visits. Acupuncturists will not know whether their patients are in the SA or EA group until 10 weeks into the standard treatment period. For qualitative data collection, interviewers are expected to be unmasked to participants treatment condition. No members of the Core Executive Team (Multiple PI's, site PI's and the Statistical Methods Committee, which includes the study biostatisticians) will have access to the outcomes data during the course of the trial. Conceivably, a site PI or one of the Multiple PI's may become aware of an individual's treatment group if they have an Adverse Event that requires the investigator intervene. However, one biostatistician, [name], will be partially unblinded only to the proportion of missing data by masked intervention group and other baseline characteristics by masked intervention group which are included in the closed report of the DSMB. [name] will not have direct access to the actual outcome data or any information about the distribution of the non-missing outcome data and is only lending statistical expertise to ongoing trial monitoring and reporting for purpose of correspondence with the DSMB and NIH. All other members of the CET will become unblinded after the data base is locked. All primary outcome analyses for the main results paper of the trial will be conducted by a fully blinded biostatistician, [name].

## **8. Multiple Comparisons**

We have one primary outcome – the change on RMDQ scores for low-back pain related disability at 6 months since baseline. To control for multiple comparisons due to 3 intervention groups we will apply Fisher's Least Significant Difference approach in which first an omnibus Wald-test for any statistically significant difference

between the three groups is evaluated at the 0.05 alpha level. If the omnibus test is statistically significant, then the pair-wise differences are then evaluated, each using two-sided alpha=0.05. If the omnibus test is not statistically significant, we will conclude that there is no benefit of acupuncture for that time point. In addition, secondary analyses will use a similar approach as that described for the primary outcome to control for the three group comparisons.

